#### Remote exercise course

Increasing physical activity has been supported in the recent review to inform the 2021 EULAR recommendations for lifestyle improvements in rheumatology patients (21). Significantly improved fatigue scores were found in an aerobic exercise group compared to a control group (22), and another recent study found exercise led to improvements in various outcomes including QoL (23). Importantly, exercise was also found by Kao et al to not exacerbate disease activity in SLE (24). We will be trialling an online (Zoom), combined Pilates and yoga instructor-led course, adapted for patients with SARDs with the focus on MH health and participation. This type of more gentle exercise has been trialled in both SLE (25) and other SARDs (26) with positive findings on physical measures. Our intervention and assessment measures will be focusing more on the Impact on mental and psychosocial health, which are currently very under-researched areas.

#### Listening therapy

Several studies have assessed effectiveness of formal counselling and cognitive behavioural therapy (27) and mindfulness (28) in SLE. Outside of trials, these types of therapy are often prohibitively expensive to either the NHS or to the individual, making them unlikely to be cost-effective to include as part of SLE care, however effective and acceptable. One of our interventions will therefore be a charity run project, The Wren Project, that provides free listening support to patients with autoimmune diseases, and potentially represents a more sustainable cost-effective method of support. The listening support is provided by trained volunteers with the focus on a safe space for patients to talk about their disease and impact on their lives. Although patients report a high level of satisfaction with the listening support provided by the Wren Project, acceptability and the impact in improving people's lives including in reducing loneliness and increasing resilience has yet to be formally evaluated.

#### Text message programme

Research indicates mobile health technology in lupus is of increasing interest (29) and Ra et al reported a "desire [for] increased diversity in the methods of delivering digital SLE information" (30), yet currently available tools were felt to be of poor quality (29). As far as we are aware, no studies have trialled text messaging support and education in SLE. Evidence of potentially high acceptability of a text programme was found in our Covid and shielding study (31) demonstrating a high acceptability and perception of 'care' and support from Government generic texts to the clinically extremely vulnerable.

We have found a large disparity in patient satisfaction with rheumatology medical care, particularly apparent amongst those living in the devolved nations (7). Educational text messages from the most eminent UK specialists will allow their knowledge to be disseminated to any UK patient, regardless of location, leading to a reduction in inequalities of care. Patient self-management and knowledge will be improved leading to potential improvements in physical outcomes, and the effect on patient MH and feeling supported will likely be enhanced by regular text messages from peers, psychologists and clinicians. The Behavioural Science group at Cambridge has carried out many successful text messaging interventions in a variety of patient groups (32, 33) and will utilise that expertise to develop a programme tailored to the needs of this patient group. Text messaging programmes are extremely cost-effective and once the programme has been designed can be easily incorporated into usual care if the trial is found to be effective.

## 6. The 'ADAPT' study

6.1 Study aims, objectives and progression

#### Aim

To assess the acceptability, feasibility and effectiveness of methods of remote psychosocial support for SARDs patients. For the interventions trialled (if effective and acceptable) to be incorporated as an adjunct to usual care.

#### **Objectives**

- To trial multiple quality of life and mental health measures to determine the most appropriate primary and secondary outcomes for phase 2.
- To test processes to inform phase 2 effectiveness trial.
- To develop and trial our own ADAPT instrument to more accurately reflect, measure and monitor SARD patient personal, social and medical satisfaction.
- To assess the acceptability (phase 1) and effectiveness (phase 2) of remote psychosocial interventions on the mental health, wellbeing, self-esteem, resilience, loneliness and disease acceptance of patients with systemic autoimmune rheumatic diseases.

## Progression of interventions to phase two.

In phase one, we will be evaluating various potential outcome measures for phase two whilst also ascertaining acceptability and feasibility of the three interventions to progress to phase 2. Phase two will be assessing the effectiveness of any interventions that progress to phase 2. Further selection criteria are explained below.

Interventions will only progress to phase two (effectiveness trial) if there is a high degree of acceptability and feasibility demonstrated in phase 1. Thresholds for progression to phase two are:

- 1. Green: Progress to phase 2 if >75% of phase 1 participants are satisfied/ very satisfied with the support and engaged with the support.
- 2. Amber: Consider progression to phase 2 with study team, charity, and patient group discussion, and if intervention acceptability and engagement can be feasibly improved, if between 50-75% of participants are satisfied and engaged with the support.
- 3. Red: Do not progress any intervention where <50% of participants are satisfied and engaged.

In addition, interventions that are found to not be feasible for the providers or the research team to progress to larger numbers in phase 2 will be excluded. Interventions may be trialled together for comparison or may be separate trials with separate control groups for phase two depending on phase one findings.

#### 6.2 Inclusion Criteria

Both phases - Aged 18 years and over

Phase 1: Any INSPIRE (Ethics reference: PRE2021.27) study participant reporting a diagnosis of SLE and requesting on the INSPIRE survey (completed Jul-Sep 23) to be considered for the ADAPT trial.

Phase 2: Reporting a diagnosis of any SARD.

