Eligibility criteria	Both phases - Aged 18 years and over  Phase 1: Any INSPIRE (Ethics reference: PRE2022.027) study participant reporting a diagnosis of SLE and requesting on the INSPIRE survey (completed Jul-Sep 23) to be considered for the ADAPT trial.  Phase 2: Reporting a diagnosis of any SARD
Recruitment and group allocation	For both phases, patients expressing an interest in participating in ADAPT at the end of INSPIRE survey will be emailed to confirm continued interest in participating. They will be randomly selected (until trial numbers filled) and then, once consent is given, randomly allocated (block allocation by the study statistician) into one of the intervention or control groups. If INSPIRE study participant responses do not generate sufficient ADAPT participant numbers, additional recruitment will be through online advertising via patient charities and support groups.
Description of intervention	1. Text messages. The text message intervention will be over 8 weeks for each phase and consist of regular (initially twice daily then tapering off gradually as the intervention progresses to 3 x texts a week in the final week) texts. Messages will be a mixture of informative and supportive, and include patient behavioural change techniques. Each automated text will be from named sources (rheumatologist, patient, psychologist and neuropsychiatrist). Participants will be sent the source details at the start, including photos and a link to a recorded video where the sources introduce themselves. The text message intervention will be adapted and improved from patient feedback in the pilot trial. Example texts from the planned programme include:  'Hi [patient name], other people don't always understand how bad the fatigue we get can be. Never feel bad for saying no to doing things when you need to rest!' – [name] (fellow patient)  'Please tell your rheumatologist or GP if you're having any mental health problems. Many people with lupus get them, it's nothing to be embarrassed about and your doctors can only help if you tell them' – [name] (neuropsychiatrist)  The sun can cause a flare in many lupus patients. Please use factor 50 sunscreen, cover up and avoid the sun as much as possible [name] (rheumatologist)  Hello [name], remembering to take lots of medications can be hard for anyone. If you're struggling, try using a Dossett box, setting alarms or have the tablets next to where you get breakfast so it becomes a routine' [name] (psychologist).

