#### Follow-ups

Follow-up 1 - Baseline+ 12 weeks

Follow-up 2 - Baseline + 6 months

Participants will be sent up to 3 email reminders for non-response to the follow-up questionnaires.

#### 6.7 Selection of outcome measures for phase 2

Phase 2 primary and secondary outcome measures will be selected from the analysis of phase 1 quantitative and qualitative results. Following phase 1 analysis, the multidisciplinary ADAPT study team will meet to decide which intervention(s) will proceed to phase 2 and which outcome measures to select for phase 2. The selection criteria will include (with most weight given to patient views on importance):

- 1. Acceptability and perceived importance and relevance of each measure to patients. These will be assessed quantitively by questions on the survey about each instrument, and qualitatively during interviews. Any measures that are rated as unacceptable or irrelevant by >25% of participants will be excluded. Participants will be asked to rank the measures in terms of importance to them and a mean score calculated. The top 3 scoring outcome measures will be discussed, taking into account additional patient views from interviews, team views and sensitivity as detailed below to select one measure for the primary outcome measure. Other measures will be considered for inclusion as secondary outcomes, by considering the ordering of patient scores, and patient willingness to complete different lengths of follow-up surveys. A minimum of one phase 1 outcome measure will be excluded for phase 2.
- 2. Sensitivity of each measure to change by psychosocial interventions. Short-term effectiveness of each intervention will be measured by using the within-person change from baseline to follow-up one, for each phase 1 instrument.

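### Phase 1 enrols only SLE, so it cannot meet an acceptability objective stated for all SARDs, and its verdicts pass to an any-SARD phase 2 with no planned check in other diagnoses

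*Protocol*

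**What the plan says.** **Objectives (Protocol sections 4 and 6.1).** One objective is "To assess the acceptability (phase 1) and effectiveness (phase 2) of remote psychosocial interventions", and the population it names is "loneliness and disease acceptance of patients with systemic autoimmune rheumatic diseases". Another is to develop and trial the ADAPT instrument for SARD patients.

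**Eligibility (sections 4 and 6.2).** Phase 1 takes an INSPIRE "study participant reporting a diagnosis of SLE and requesting on the INSPIRE survey". For the second phase the criterion is "Phase 2: Reporting a diagnosis of any SARD".

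**Progression (section 6.1).** "Interventions will only progress to phase two (effectiveness trial) if there is a high degree of acceptability and feasibility demonstrated in phase 1". The Green rule is "Progress to phase 2 if >75% of phase 1 participants are satisfied/ very satisfied with the support and engaged with the support". Amber is 50-75% and Red is below 50%.

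**Outcome choice (section 6.7, selection of outcome measures).** "Phase 2 primary and secondary outcome measures will be selected from the analysis of phase 1 quantitative and qualitative results". A measure that more than 25% of participants call unacceptable or irrelevant is dropped. Patients rank the measures, and the top three are discussed to choose the primary outcome.

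**Text messages (section 4).** Four example texts are given. Two mention lupus, one of them with "The sun can cause a flare in many lupus patients". The other two, on fatigue and on remembering medication, do not.

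**The concern.** The phase that is to establish acceptability in SARDs recruits from one SARD. Decisions that bind phase 2 (which interventions go forward, which measures survive, which three compete to be primary) are taken on that sample and then applied to a wider population. No passage argues that SLE results carry over to other SARDs, and none requires a check in non-SLE patients before or after the decisions are fixed.

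Two things are at stake. A phase 1 report written to the objective would claim acceptability in SARDs from SLE data alone. Phase 2 could also take forward an intervention, or a primary outcome, whose relevance to part of its population has never been examined.

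**Working it through.** **1. Sample sizes, reproduced from section 4.** Phase 1: 4 × 30 = 120. Phase 2, provisional: 100 + 100 + 300 + 300 = 800. Both match the stated totals.

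**2. Non-SLE information in phase 1.** Verdicts are given per intervention, so the base is 30. Under section 6.2 every participant reports SLE; some may have another SARD as well, but none is planned with another SARD and no SLE. The planned count is 0 of 30 in each arm. The fallback recruitment by advertising in section 6.3 does not lift the SLE criterion.

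**3. Precision within SLE.** The smallest Green count is 23/30 = 76.7%, since 22/30 = 73.3%. The exact (Clopper-Pearson) 95% interval for 23/30 is 57.7% to 90.1%. That interval describes SLE only.

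**4. What a just-Green arm could mean in phase 2.** Let s be the non-SLE share of phase 2 and q the proportion of non-SLE participants who are satisfied and engaged. Neither is in the Protocol; both are assumed here. The overall rate is (1 − s) × 23/30 + s × q.

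| s | q = 40% | q = 60% | q = 80% |
|---|---|---|---|
| 25% | 67.5% | 72.5% | 77.5% |
| 50% | 58.3% | 68.3% | 78.3% |
| 75% | 49.2% | 64.2% | 79.2% |

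Example: 0.5 × 76.7% + 0.5 × 40% = 58.3%. The same phase 1 result fits Green, Amber or Red overall. If q is 80%, the result is Green at every share shown.

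**5. The 25% rule for measures.** Assume 15% of SLE patients find a measure unacceptable, so phase 1 keeps it. If half of phase 2 is non-SLE and 50% of those find it unacceptable, the overall rate is 0.5 × 15% + 0.5 × 50% = 32.5%, above the limit. If only 10% of them do, it is 0.5 × 15% + 0.5 × 10% = 12.5%, and the measure stays.

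**6. Where the transfer is least secure.** The listening support is the provider's standard programme for autoimmune disease (section 4). The exercise course is described in section 5 as adapted for SARDs, with supporting studies in SLE and in other SARDs. Section 5 supports the text programme with SLE evidence, and half of its example texts are worded for lupus. It is also the largest intervention arm: 300 of the 500 provisional intervention places, or 60%.

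**The case against.** Piloting in one member disease and then widening is a recognisable staged design, and SLE is itself a SARD. That stands: the eligibility change is not an error in itself. The fault lies in the objective's wider claim and the unchecked transfer.

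A reader might infer that the SLE pilot's feedback is the only source of revision. It is not. Section 7.9 schedules an adaptation step before phase 2. Section 7.7 puts five patients with autoimmune rheumatic diseases on the research team and consults charity leaders. The advisory group in section 7 includes a vasculitis consultant and patient members and meets when progression is decided. The Amber rule requires charity and patient-group discussion. These inputs lessen the problem, but none measures satisfaction or engagement in non-SLE participants.

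Nor do SLE rankings alone settle the outcomes. Section 6.7 keeps EQ-5D-5L whatever phase 1 shows and keeps FACIT-F for the exercise trial unless more than 25% find it unacceptable. Team views and sensitivity to change also count in choosing the primary outcome. Even so, patient views carry most weight, and in phase 1 those are the views of people with SLE.

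Finally, section 6.6 does not confine acceptability questions to phase 1, so the study as a whole could produce non-SLE acceptability data. Such data would come after interventions and outcomes are chosen, and no separate use of them is planned.

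**Conclusion.** The point holds in limited form. Phase 1 cannot show acceptability, or the relevance of the ADAPT tool and other instruments, in SARDs other than SLE, because no planned participant has one without SLE. The objectives say otherwise, and the progression and outcome rules carry the SLE result forward untested. This rests on the text of the Protocol and on no assumption.

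The size of any consequence is unknown. The percentages above depend on assumed shares and rates, and show only that a Green verdict does not settle the matter. A reader might infer that the phase 2 treatment effect would be diluted, or that a Green verdict would be wrong for the wider population. The documents support neither, since they say nothing about how non-SLE patients would respond, and a similar response would leave the verdict unchanged. The concern also does not fall equally on all arms: it is strongest for the text messages.

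**What to change.** 1. In sections 4 and 6.1, restate the phase 1 acceptability objective, and the ADAPT-tool objective as far as phase 1 serves it, as applying to SLE. Acknowledge that phase 2 extends the results to other SARDs.
2. In phase 2, use the acceptability questions already planned in section 6.6 to report satisfaction and engagement separately for SLE and for other SARDs, against the existing >75%, 50-75% and <50% thresholds, before recommending any intervention for SARDs.
3. Before phase 2, have the lupus-specific wording of the texts reviewed with patient members who have a SARD other than SLE. The Protocol does not give the members' diagnoses, so confirm that the group includes such patients.
4. Optionally, stratify phase 2 randomisation by SLE versus other SARD.

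**Cost.** Two objectives are reworded, one table and a short wording review are added, and the phase 1 claim becomes narrower. Precision in the non-SLE group will be limited. With an assumed non-SLE share of 25%, an arm of 100 holds about 25 such participants, and even 30 gives an interval as wide as 57.7% to 90.1% at 23/30.

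Two larger changes are not recommended. Opening the 120 phase 1 places to any SARD would split arms of 30 across several diseases. Writing a separate text programme for each diagnosis would be costly.

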#### 6.3 Participant recruitment

For both the phases, patients who expressed an interest in participating in ADAPT at the end of the INSPIRE survey will be emailed with an ADAPT information sheet to confirm continued interest in participating in ADAPT. They will be randomly selected (until trial numbers filled) and then randomly allocated by the study statistician using block randomisation into one of the intervention or control groups. If INSPIRE study participant responses do not generate sufficient ADAPT participant numbers, additional recruitment will be through online advertising via patient charities and support groups and then randomly allocated to intervention groups. If numbers interested in phase 1 exceed study capacity, those participants will be emailed to be informed they were not randomly selected to

participate in phase 1 but will be invited to apply again for phase 2 if interested. Exact sample sizes for phase 2 will be calculated from phase 1 effectiveness result indications. Phase 1 participants will not be eligible for phase 2 participation.

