#### 7.9 Proposed study timetable and proposed outputs

	2023			2024				2025
	Jan 2023	April 23	May- Dec 23	Jan- Mar 24	Apr- Jul 24	Aug- Oct 24	Nov - Dec 24	2025
Produce draft protocol	Х							
Finalise participant information sheets and surveys	x							
Submit ethics proposal	Χ							
Trial surveys	Х							
INSPIRE Ppts who expressed interest in ADAPT contacted and randomised if consenting to participate		х						
Interventions commence.  Text messages and controls: All commence in /May 23  The Wren project: 5 ppts commence intervention per month  Online exercise: First group of 15 ppts commences in Apr, second group in Sep 23			х					
Interviews with selected participants		х	Х	х				

Follow-ups at individual ppts F-up 1 and 2 points		Х					
Final follow-up 2s for later intervention ppts (initially controls)			х				
Initial analysis and assessment of adaptions to interventions required for phase 2, and development of stage 2 interventions			х	х			
Phase 2 commences					х		
Phase 2 follow-ups						Х	Х
Quantitative and overall analysis (separate analysis for each phase and combined final analysis) and draft papers				х	х	х	х
Qualitative analysis (ongoing throughout interventions and post-intervention in-depth interviews	х	х	х	х	х	х	х
Publications					Х		Х

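### The phase 1 inclusion criterion rules out the advertised recruits that section 6.3 allows, and section 6.3 allocates such recruits without naming the control group

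*Protocol*

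**What the plan says.** Section 6.2 defines a phase 1 entrant as an adult INSPIRE "study participant reporting a diagnosis of SLE and requesting on the INSPIRE survey (completed Jul-Sep 23) to be considered for the ADAPT trial". The eligibility row of the synopsis (section 4) carries the same restriction. For phase 2, section 6.2 asks only for adulthood and a SARD: "Phase 2: Reporting a diagnosis of any SARD".

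Section 6.3 opens by covering both phases: "For both the phases, patients who expressed an interest in participating in ADAPT at the end of the INSPIRE survey will be emailed". These INSPIRE recruits are then "randomly allocated by the study statistician using block randomisation into one of the intervention or control groups". For a shortfall, the same section says that "additional recruitment will be through online advertising via patient charities and support groups and then randomly allocated to intervention groups". The synopsis has the same fallback, also introduced for both phases but with no allocation clause of its own: "If INSPIRE study participant responses do not generate sufficient ADAPT participant numbers, additional recruitment will be through online advertising via patient charities and support groups". Section 6.4 (Consent) likewise provides for putting the study materials online if INSPIRE does not yield enough people, with no limit to phase 2.

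The data collection part of the synopsis places the baseline survey before randomisation. It describes that randomisation as covering control as well as the interventions and makes no exception by recruitment source.

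On dates, section 1 dates version 1 at 17/02/23, and the section 7.9 timetable has this step under April 23: "INSPIRE Ppts who expressed interest in ADAPT contacted and randomised if consenting to participate".

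**The concern.** There are two separate faults, and both lie in rules that the protocol itself fixes.

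The first is eligibility in phase 1. Staff who need to fill the 120 places by advertising must break either section 6.2 or section 6.3. The SLE requirement for phase 1 is also written only inside the sentence about INSPIRE participants. If section 6.3 is taken to override section 6.2, no diagnosis criterion is left for an advertised phase 1 recruit.

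The second is allocation. Two neighbouring sentences in section 6.3 give different destinations. INSPIRE recruits go by block randomisation to an intervention or to control. Advertised recruits go at random to intervention groups, a term that the synopsis sample-size entry uses for the three active arms as distinct from control. If a trial team followed that wording, control would hold INSPIRE respondents only, while the active arms would mix them with volunteers from charities and support groups. Every comparison with control would then also compare recruitment sources. Loneliness and community support are among the measured outcomes, so a difference between sources is plausible, though the protocol gives no data on it.

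**Working it through.** **Eligibility, passages side by side.**
- Phase 1: the criterion requires INSPIRE participation and a request made on the INSPIRE survey. The fallback admits people without either. One person cannot satisfy both rules, so they contradict.
- Phase 2: the criterion requires age 18 or over and any SARD. An advertised volunteer with a SARD meets it, so there is no contradiction.

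**Allocation, passages side by side.**
- Section 6.3, INSPIRE recruits: block randomisation, intervention or control.
- Section 6.3, advertised recruits: random allocation, intervention groups; control and blocking not mentioned.
- Synopsis, data collection: entrants randomised to an intervention or control.
- Synopsis, recruitment: no separate rule for advertised recruits.

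The second item conflicts with the third.

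**The plan's own totals.** Phase 1: 3 × 30 + 30 = 120, as stated. Phase 2 (provisional): 100 + 100 + 300 + 300 = 800, as stated.

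**What the literal wording would do in phase 1 (illustration).** Let *a* be the number of advertised recruits among the 120, and *d* the difference between sources in the outcome as analysed, in SD units. The protocol states neither, so the values of *a* and *d* = 0.5 are assumptions. With arms held at 30, all advertised recruits fall in the 90 intervention places. The share is *a*/90, and the bias in an intervention-versus-control contrast is (*a*/90) × *d*. Under randomisation to all four arms, the expected share is *a*/120 in every arm and the expected bias is zero.

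| *a* | Share in intervention arms, literal | Share in control, literal | Bias at *d* = 0.5 | Share in every arm, four-arm randomisation |
|---|---|---|---|---|
| 6 | 6/90 = 6.7% | 0 | 0.03 SD | 5% |
| 12 | 12/90 = 13.3% | 0 | 0.07 SD | 10% |
| 30 | 30/90 = 33.3% | 0 | 0.17 SD | 25% |
| 60 | 60/90 = 66.7% | 0 | 0.33 SD | 50% |

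The general rule is share × difference: 0.20 × 0.5 = 0.10 SD and 0.40 × 0.5 = 0.20 SD.

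Holding arms at 30 means that INSPIRE recruits are not split equally. If they are split equally over four arms and the advertised recruits are added to the active arms only, then with *a* = 30 control has (120 − 30)/4 = 22.5 and each intervention arm has 22.5 + 30/3 = 32.5. The planned 30 per arm is lost. The share is 10/32.5 = 30.8% and the bias is 0.308 × 0.5 = 0.15 SD.

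**Dates.** The criterion places the INSPIRE survey in Jul-Sep 23. That is after the protocol date of 17/02/23 and after the April 23 contact and randomisation of people who had already answered the survey.

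**The case against.** A reader might infer more than the documents support, in four ways.

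*Every advertised recruit is ineligible.* This is true only for phase 1. Phase 2 has no INSPIRE requirement.

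*The trial means to keep advertised recruits out of control.* The documents point the other way. The synopsis describes randomisation that includes control, and section 6.3 calls the allocation of advertised recruits random. A fallback meant to reach the trial's numbers could never fill a shortfall among the 30 controls if control were closed to it. The phrase is most plausibly shorthand for the study groups. This largely stands. What remains is that section 6.3 is the operative allocation text and differs from the synopsis.

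*The arms will be biased by a stated amount.* The top-up share and the source difference are both assumed. Sections 6.7 and the analysis section also use within-person change, where a stable difference in level between sources would largely cancel, so *d* would have to be a difference in change. Phase 1 progression rests on satisfaction and engagement, and sensitivity to change is judged within person; neither needs the control contrast. The fallback may not be used at all, since section 6.3 also plans for too many volunteers. All of this limits the consequence in phase 1. It does not remove it, because section 6.3 sizes phase 2 from phase 1 indications of effectiveness and the same allocation sentence governs the phase 2 effectiveness trial.

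*Nobody is eligible because of the survey date.* The protocol treats the survey as completed and already uses INSPIRE results, so the date is evidently a slip. It is a separate editorial matter and adds nothing to the allocation argument.

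**Conclusion.** The point holds as an internal inconsistency that should be corrected. The eligibility contradiction is certain on the text and confined to phase 1. The allocation wording conflicts with the synopsis in either phase. If followed literally, and only if the fallback is used, it confounds recruitment source with intervention versus control; comparisons among the three interventions are not affected in the same way. The documents do not show that intervention-only allocation is intended.

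The size of any bias cannot be derived from the protocol. The illustrative range of 0.03 to 0.33 SD rests on an assumed 6 to 60 advertised recruits out of 120, arms held at 30, and an assumed 0.5 SD difference between sources in the analysed outcome.

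**What to change.** 1. Reconcile section 6.2 and the synopsis eligibility row with sections 6.3 and 6.4 and the synopsis recruitment row. Either of two changes does this: limit the advertising fallback to phase 2, or extend the phase 1 criterion to advertised recruits aged 18 or over with reported SLE. The choice is the sponsor's.
2. Whichever is chosen, reword section 6.3 so that advertised recruits are allocated by the same block randomisation as INSPIRE recruits, into one of the intervention groups or control.
3. Reconcile the Jul-Sep 23 survey date, in section 6.2 and the synopsis, with the protocol date of 17/02/23 and the April 23 randomisation.

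The cost is a few sentences of protocol wording and an ethics notification. The planned totals and arm sizes do not change, and no extra participants are needed.
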